4.4 Secondary Objectives

4.4.1 Tenofovir PK

Purpose: (Secondary Objective 1) To assess the impact of LDV/SOF and HIV PI/r co-administration

Note: The tenofovir PK analysis will be described and conducted by the study pharmacologist separately.

4.4.2 HCV Virologic Responses

Purpose: (Secondary Objective 3 and 8) To assess the proportion of participants who attain SVR4 and SVR24 in each study arm. To evaluate kinetics of HCV RNA during treatment and after treatment discontinuation.

- a) Listing of each participant's HCV RNA results will be provided with calculated visit weeks.
- b) Number and percent of participants with SVR4 with a two-sided 90% confidence interval.
- c) Number and percent of participants with SVR24 with a two-sided 90% confidence interval. (SAP Version 2: This will be provided as part of SVR24 supplement to the Primary Final Analysis Report.)
- d) Number of participants with relapse.

Notes:

1. SVR4 is defined in the protocol as HCV RNA < LLOQ (either TD or TND) at 4 weeks after treatment discontinuation. The sample within the week R+4 visit window, as described in Section 2.6, which is closest to the targeted time will be used. If there is no HCV RNA sample within this window, then the participant will be considered SVR4 failure, unless there are preceding and subsequent HCV RNA measurements that are both <LLOQ (either TD or TND).
 2. SVR24 is defined in the protocol as HCV RNA <LLOQ (either TD or TND) at 24 weeks after treatment discontinuation. Sample after 20 weeks after treatment discontinuation that is closest to the targeted, not followed by any result \geq LLOQ, will be used.
 3. Relapse is defined as <LLOQ (either TD or TND) for the latest HCV RNA result prior to the end of study treatment and HCV RNA \geq LLOQ after treatment at a subsequent visit.
- ✓ SDAC validation: All programs generating variables as study-specific will be validated (e.g. HCV RNA variable for each study visit, HCV relapse, SVR4 and SVR24).

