NOTE: Inability to definitively determine genotype or a non-GT-1 will exclude the participant from study participation.

4.1.8 Prior virologic treatment failure with SOF-containing regimen (SOF/RBV, SOF/PEG/RBV, and SOF/SIM).

NOTE A: See section 6.3.3 for requirements for documentation of prior HCV treatment and response.

NOTE B: Prior virologic failure is defined as quantifiable HCV RNA at any time after receiving HCV therapy as prescribed that was not attributed to reinfection.

NOTE C: HCV reinfection is defined by (1) documentation of clearance of prior infection (as evidenced by prior positive anti-HCV Ab or HCV RNA) either spontaneously or after treatment with two negative HCV RNA a minimum of 3 months apart AND (2) positive HCV RNA after documentation of two negative HCV RNA obtained a minimum of 3 months apart *or* infection with a different HCV genotype from the prior infection.

4.1.9 Body mass index (BMI)  $\geq$  18 kg/m^2 within 42 days prior to study entry.

NOTE A: A BMI calculator is available at the DMC website (http://www.fstrf.org).

NOTE B: The height and weight measurement used to calculate BMI must be obtained on the same day.

- 4.1.10 The following laboratory values obtained within 42 days prior to study entry by any US laboratory that has a CLIA certification or its equivalent.
  - HCV RNA  $\geq 10^4$  IU/mL
  - Hemoglobin  $\geq$  12.0 g/dL for male,  $\geq$ 11.0 g/dL for female participants
  - Platelets  $\geq$  50,000/mm^3
  - International normalized ratio (INR) ≤1.5 x ULN unless participant has known hemophilia or is stable on an anticoagulant regimen affecting INR, in which case any INR value is acceptable
  - Albumin ≥ 3.0 g/dL
  - Creatinine clearance (CrCl) ≥ 60 mL/min, as calculated by the Cockcroft-Gault equation (refer to section 6.3.5 for calculator utility link)
  - Aspartate aminotransferase (AST) (SGOT) < 10 x ULN
  - Alanine aminotransferase (ALT) (SGOT) < 10 x ULN
  - Direct bilirubin  $\leq 1.5 \times \text{ULN}$
  - Hgb A1C ≤ 8.5%
- 4.1.11 Screening electrocardiogram (ECG) without clinically significant abnormalities as determined by the investigator within 42 days prior to study entry.
- 4.1.12 Willing and able to provide written informed consent.

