#### 6.2.4 Event Driven Evaluations

## HCV Virologic Failure/Relapse Confirmation

Participants with suspected HCV VF, as defined in section 7.3, must have a confirmation sample obtained as soon as possible, but within 2 weeks of initial notification of HCV RNA meeting criteria for HCV VF. Participants who permanently discontinue study treatment for HCV VF (see details in section 7.3) will be followed on study/off treatment in Step 2 per the SOE.

Virologic evidence of HCV relapse, defined as HCV RNA <LLOQ at end-oftreatment but HCV RNA ≥LLOQ during follow-up, will require confirmation and the sample should be obtained and the sample sent in real time to the designated laboratory as soon as possible but within 2 weeks after determination of initial observation. The results will be provided to the site investigators within 2 weeks of specimen receipt.

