#### HCV Genotype

At screening, the HCV genotype and subtype result will be obtained locally from any laboratory that has a CLIA certification or its equivalent. ONLY IF IT IS NOT AVAILABLE LOCALLY should it be done at the designated testing laboratory (see A5348 LPC).

Stored plasma will be collected at the entry visit for additional testing and may be used for HCV genotype testing if confirmation of genotype is requested by the study team.

HCV genotype sample collected at the time of HCV viral failure confirmation will not be performed locally, but should be collected and shipped as per the LPC.

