4.2.5 Virologic Failures

- a) HIV Virologic Failure

- Details on participants on ART with undetectable HIV RNA at entry who experience HIV-1 virologic failure (as defined in the protocol), including adherence to study regimen and ARV medications, and dose modifications to study medications and ARVs.
- b) HCV Virologic Failures
 - Details on participants who experience HCV virologic failure (as defined in the protocol), including ARV regimen, adherence to study regimen and ARV medications, dose modifications to study medications and ARVs, and the following baseline information: HCV RNA, cirrhosis status, race and ethnicity, HCV genotype, development of resistance-associated variant at the time of virologic failure.
- ✓ SDAC validation: All programs generating variables as study-specific will be validated (e.g. HIV breakthrough, HCV breakthrough).

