4.3 Primary Objectives

4.3.1 SVR12

Purpose: To address the primary HCV virologic response objective to assess the proportion of participants who attain SVR12 in each study arm.

- a) Two-sided 90% confidence interval around the observed SVR proportion using the Wilson confidence limits, per protocol.
- b) Two-sided 95% confidence interval around the observed SVR proportion using Clopper-Pearson limits, to line up with the Gilead study (in consideration of joint manuscript).
- c) For the non-SVRs, reasons for failure will be provided: detectable HCV RNA after treatment discontinuation, HCV virologic failure (VF) as determined by the site, unavailable HCV RNA result, other.

Note on the primary HCV virologic endpoint:

1. SVR12 is defined in the protocol as HCV RNA < lower limit of quantification (LLOQ), either target detected (TD) or target not detected (TND), at 12 weeks after treatment discontinuation. The sample within the week R+12 visit window, as described in Section 2.6, which is closest to the targeted time will be used. If there is no HCV RNA sample within this window, then the participant will be considered SVR12 failure, unless there are preceding and subsequent HCV RNA measurements that are both <LLOQ (either TD or TND).
 2. Participants not providing SVR data (e.g. due to early study discontinuation) will be included and counted as SVR failures.
- ✓ SDAC Validation: Derivation of SVR12 variable will be validated. The analysis program that summarizes SVR12 and calculates confidence intervals will also be validated.
 - ✓ Data sources for the primary endpoint SVR12: HCVRNALDMS (LDMS data table), F1601 (off study CRF table), F4003 (off treatment CRF table), F0010 (patient visit CRF data table),

STATUS (data table on key patient characteristics and date variables including date of last dose of study treatment), CMW0029 (concomitant medication CRF table to censor data at initiation of alternate HCV treatment in case any participants erroneously remained on study when alternate HCV treatment was initiated), SPW0455 (HCV RNA specimen tracking CRF table).

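### The SAP defines relapse by unconfirmed HCV RNA alone, so a reinfection after treatment would be counted as LDV/SOF relapse

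*SAP*

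**What the plan says.** SAP 4.4.2(d) plans one output on this point, "Number of participants with relapse", and Note 3 defines it: "Relapse is defined as <LLOQ (either TD or TND) for the latest HCV RNA result prior to the end of study treatment", then HCV RNA at or above LLOQ at a visit after treatment. The derived relapse variable is among those to be programmed and validated.

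The protocol uses the same RNA rule but adds a condition. Section 6.2.4 reads: "Virologic evidence of HCV relapse, defined as HCV RNA <LLOQ at end-oftreatment but HCV RNA ≥LLOQ during follow-up, will require confirmation".

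The protocol recognises reinfection, but only for eligibility. Section 4.1.8 NOTE B defines prior virologic failure as quantifiable RNA "that was not attributed to reinfection". NOTE C describes reinfection as documented clearance plus either a positive RNA after two negatives at least 3 months apart or "infection with a different HCV genotype from the prior infection".

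The data that could separate the two events are scheduled. The protocol's schedule of events puts genotype and resistance testing at HCV failure confirmation. Section 6.3.8 says: "HCV genotype sample collected at the time of HCV viral failure confirmation will not be performed locally". Resistance is also tested at entry, and entry plasma is stored and may be used to confirm genotype.

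The SAP does not use the failure genotype. SAP 4.2.5(b) lists failures with ARV, adherence and dose details "and the following baseline information: HCV RNA, cirrhosis status, race and ethnicity, HCV genotype, development of resistance-associated variant at the time of virologic failure", so genotype appears there as a baseline item. SAP 4.3.1(c) says: "For the non-SVRs, reasons for failure will be provided: detectable HCV RNA after treatment discontinuation", then site-determined virologic failure, unavailable result and other. Reinfection is not mentioned anywhere in the SAP.

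**The concern.** The protocol asks whether earlier viraemia was reinfection before it counts a patient as a treatment failure at entry. The SAP does not ask this of viraemia after study treatment. A participant who clears the virus and acquires a new one during follow-up meets Note 3 in full and is reported as a relapse on LDV/SOF.

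Dropping confirmation is a second gap. Read literally, Note 3 lets one unconfirmed quantifiable result make a relapse, although the protocol requires a second sample.

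At stake is the account of why retreatment fails. Protocol 9.6 treats the reasons for missing SVR12 as an important supplement to the primary analysis, and objective 1.3.7 concerns resistance emerging in SVR12 failures. SAP Version 2.0 intends the results to contribute to a company manuscript on a similar trial, so a wrong label could travel beyond this report.

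**Working it through.** **Rules side by side**

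| Item | Protocol, at entry (4.1.8) | Protocol, on study (6.2.4) | SAP (4.4.2 Note 3) |
|---|---|---|---|
| Based on HCV RNA | yes | yes | yes |
| Confirmatory sample | not stated | required | not stated |
| Reinfection excluded | yes | no | no |
| Failure genotype or sequence used | not applicable | collected | not used |

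I take the schedule's failure-confirmation column to cover relapse, because protocol 6.2.4 handles failure and relapse confirmation under one heading.

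**Could RNA timing alone identify reinfection?** NOTE C's other route needs two negatives at least 3 months apart, about 365.25/4 = 91 days. SAP 2.6 gives R+4 as R+23 to R+35 and R+12 as R+79 to R+98.
- Viraemia first seen at R+12: the only scheduled post-treatment negative before it is R+4, so there are not two.
- Viraemia first seen at R+24: the R+4 and R+12 negatives are at most 98 − 23 = 75 days apart, short of 91.

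Scheduled post-treatment RNA therefore cannot meet that route. Genotype or sequence is the practical discriminator.

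**Checking the interval method.** Protocol Table 9-1 uses the two-sided 90% Wilson interval with z = 1.645:

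centre = (p + z²/2n)/(1 + z²/n); half-width = z·√[p(1−p)/n + z²/4n²]/(1 + z²/n).

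For 18/20 this gives (73.8%, 96.6%), as printed. The other six rows also reproduce.

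**Effect of one case, n = 7 (SAP 2.1).** The SAP plans only a count for relapse; I apply its 90% Wilson interval to show precision.
- 0/7: upper limit = z²/(n + z²) = 2.706/9.706 = 27.9%, so 0% (0–27.9%).
- 1/7 = 14.3%: centre = (0.1429 + 0.1933)/1.3865 = 0.242; half-width = 1.645·√(0.01749 + 0.01380)/1.3865 = 0.210; interval 3.3–45.2%.

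The documents do not give the split by arm. If it is 3 and 4, one case is 1/3 = 33.3% (7.8–74.6%) or 1/4 = 25.0% (5.8–64.4%).

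**Chance of at least one case.** The rate is an assumption, since the documents give none. Exposure = 7 × 24/52 = 3.23 person-years; P = 1 − exp(−rate × 3.23).

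| Assumed rate per 100 person-years | P(at least one) |
|---|---|
| 1 | 3.2% |
| 5 | 14.9% |
| 10 | 27.6% |
| 15 | 38.4% |

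**Effect on SVR12.** None. Quantifiable RNA in the R+12 window is failure whatever its cause.

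**The case against.** The best defence is that the SAP takes its RNA-only rule from the protocol, which has no reinfection exclusion on study either. That is right about the origin. It does not explain the missing confirmation, and it leaves the count open to the same error.

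The second defence is practical. Version 2.0 is descriptive, every participant's HCV RNA is listed, and stored plasma allows sequencing later. This limits the harm. But Note 3 gives the validated relapse variable no genotype input, so the count comes out the same whatever later work shows.

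Four stronger readings are tempting and are not supported.
- **That reinfections will be reported as emergent resistance.** SAP 4.4.3 lists targeted mutations in any sample alongside SVR12 outcome. It has no emergent flag, and baseline mutations are listed under 4.1.4. The risk is one of reading, and only if the new virus carries a targeted mutation absent at entry. The objective concerns SVR12 failures, so viraemia first seen at R+24 in an SVR12 responder falls outside that set.
- **That the reasons table mislabels the event.** The wording in 4.3.1(c) is neutral as to cause and includes a category for other reasons. It lacks a place for reinfection but does not call it relapse.
- **That a different genotype alone settles the matter under the protocol.** NOTE C also asks for documented clearance, and how its conditions combine is unclear. It is an eligibility rule, not an outcome definition.
- **That one case would be half of an arm's failures.** That uses 2 expected failures in 20, from a sample size that was abandoned. SVR12 failures also include loss to follow-up, so they are not all resistance samples.

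There is also a fair warning about the remedy. Screening subtype is normally a local result and the failure test is not local. A bare subtype mismatch could be an assay difference, and acting on it could remove a true relapse and flatter the regimen.

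**Conclusion.** The concern holds, within limits. Followed as written, Note 3 counts a reinfection as relapse, and it does so without the confirmation that the protocol requires. The damage is confined to a descriptive secondary count and, in a narrower set of cases, to how the resistance listing is read. Primary SVR12 does not change.

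One case among 7 moves relapse from 0% to 14.3%, with wide and overlapping intervals. Whether such a case occurs is unknown, and the 3–38% range rests wholly on the assumed rates. It also takes 24 weeks at risk for all 7. Because the primary report is due once SVR12 is complete and the planned supplement is an SVR24 table, a late case would enter the relapse count only if that count is run again.

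**What to change.** In SAP 4.4.2 Note 3, define relapse as confirmed post-treatment HCV RNA at or above LLOQ, after a last on-treatment result below LLOQ, with no evidence of reinfection on comparing entry and failure samples.

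State what counts as evidence: a different genotype, or an unrelated sequence on the scheduled entry and failure resistance testing, with the criterion for unrelated set before the data are examined. The protocol does not spell out that the resistance test yields sequence; if it does not, use the stored plasma. A mismatch between local and central subtype should count only after it is confirmed on stored entry plasma.

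Then:
- report reinfections on a separate line in 4.4.2 and keep them as SVR failures wherever the RNA result makes them so;
- add failure genotype to the 4.2.5(b) listing and say that the listing covers post-treatment cases, since SAP 2.3 frames virologic failure as a trigger for stopping treatment;
- add reinfection to the reasons in 4.3.1(c);
- flag reinfected participants in 4.4.3.

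The cost is SAP wording, a listing column and a little programming, plus possible retesting of stored plasma in a discordant case. No new sample is needed and the primary endpoint is untouched.

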7.3 HCV Virologic Response-Based Stopping Criteria and Confirmation of VF/Relapse

The following on-treatment HCV virologic response-based treatment stopping criteria will be utilized for all participants:

- Confirmed increase in HCV RNA ≥LLOQ if HCV RNA previously declined to <LLOQ (detected or not detected). This will be defined as HCV breakthrough.
- Confirmed ≥1 log10 IUmL HCV RNA on-treatment increase from nadir.
- Confirmed HCV RNA ≥LLOQ at week 8 visit.

Confirmation will be required for all stopping criteria and should be performed as soon as possible but within 2 weeks after determination of initial observation (see HCV VF Confirmation in section 6.2.4).

HCV RNA measurement to confirm treatment failure or relapse after treatment will be performed in real time at the designated laboratory and the results will be provided to the site investigators within 2 weeks of specimen receipt. If treatment failure is confirmed, then all study treatment should be stopped. However, participants should be followed as per section 6.2.4.

Retreatment of HCV virologic failures will not be provided through A5348.

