The study regimens have different treatment durations and, while the post-treatment follow-up time is the same for both study arms, the study durations are different in Arms A and B. Assessment of reasons for not achieving SVR12 is an important part of SVR12 and SVR24 analyses in this study, including loss to follow-up. Differential loss to follow-up in the two study arms may suggest the benefit of the shorter duration in the 12-week regimen or drawback of RBV intolerance. Either way, the SVR endpoints would capture the outcome of the regimen.

- 9.2 Outcome Measures
  - 9.2.1 Primary Outcome Measures
    - 9.2.1.1 SVR12 defined as HCV RNA < lower limit of quantification (LLOQ) (either target detected [TD] or target not detected [TND]) at 12 weeks after treatment discontinuation. The sample within the week R+12 (post-treatment) visit window, as defined in section 6.0, which is closest to the targeted time will be used. If there is no HCV RNA sample within this window, then the participant will be considered SVR12 failure, unless there are preceding and subsequent HCV RNA measurements that are both <LLOQ (either TD or TND).

    - 9.2.1.2 Occurrence of Grade 3 or higher AE (diagnosis, sign, symptom, or laboratory abnormality), SAE according to ICH criteria, or AE reported as the reason for permanent discontinuation of study treatment, during study treatment and up to 30 days after study treatment discontinuation. (Event that is ongoing at the same grade from prior to study treatment initiation will be excluded.)
  - 9.2.2 Secondary Outcome Measures
    - 9.2.2.1 Renal toxicity: (a) ≥ Grade 2 creatinine clearance after study entry, or
       (b) new proteinuria and/or glucosuria, defined as ≥ 1+ or an increase ≥ 1+ from baseline.
    - 9.2.2.2 SVR4 defined as HCV RNA < LLOQ (either TD or TND) at 4 weeks after treatment discontinuation. The measurement within the week R+4 visit window that is closest to the targeted time will be used. If there is no HCV RNA sample within this window, then the participant will be considered SVR4 failure, unless there are preceding and subsequent HCV RNA measurements that are <LLOQ (either TD or TND).

- 9.2.2.3 SVR24 defined as HCV RNA < LLOQ (either TD or TND) at 24 weeks after treatment discontinuation. Sample after 20 weeks after treatment discontinuation that is closest to the targeted time, not followed by any result ≥LLOQ, will be used.

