2.3 Study Treatment Discontinuation According to HCV Virologic Response

Study treatment will be discontinued in participants who experience confirmed HCV virologic failure (VF) defined as follows.

- a) Confirmed increase in HCV RNA to ≥LLOQ if HCV RNA previously declined to <LLOQ (target detected or not detected).
- b) Confirmed ≥1 log₁₀ IU/mL HCV RNA increase from HCV viral load nadir.
- c) Confirmed HCV RNA ≥LLOQ at week 8 visit.

Confirmatory HCV RNA sample should be obtained as soon as possible and no more than 2 weeks after receiving initial HCV RNA result. HCV RNA measurement to confirm failure will be performed in

real time at the designated laboratory and the results will be provided to the site investigators within two weeks of specimen receipt. Participants who experience confirmed HCV VF will discontinue study treatment and are followed on-study/off-treatment for 24 weeks post treatment discontinuation (Step 2).

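### SAP 4.4.2 Note 3 counts relapse on a single post-treatment HCV RNA value, whereas Protocol 6.2.4 and 7.3 require the value to be confirmed on a second sample

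*SAP*

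**What the plan says.** The SAP's relapse rule is in 4.4.2, Note 3. The first half is: "Relapse is defined as <LLOQ (either TD or TND) for the latest HCV RNA result prior to the end of study treatment". The second half asks for HCV RNA at or above LLOQ "after treatment at a subsequent visit". The rule feeds item (d) of that section: "Number of participants with relapse". Relapse is also named among the derived variables whose programs will be validated.

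Protocol 6.2.4 describes the same sequence, below LLOQ at end of treatment and at or above LLOQ in follow-up. It adds that this "will require confirmation and the sample should be obtained and the sample sent in real time to the designated laboratory as soon as possible", within 2 weeks of the initial observation. Protocol 7.3 also covers relapse: "HCV RNA measurement to confirm treatment failure or relapse after treatment will be performed in real time at the designated laboratory".

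For failure on treatment the SAP keeps the requirement. Section 2.3 states: "Study treatment will be discontinued in participants who experience confirmed HCV virologic failure (VF) defined as follows". Each of its three criteria calls for a confirmed result.

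The primary endpoint has its own rule. Protocol 9.2.1.1 opens with "SVR12 defined as HCV RNA < lower limit of quantification (LLOQ) (either target detected [TD] or target not detected [TND]) at 12 weeks after", counted from the end of study drug, and SAP 4.3.1 repeats it. Both use the one sample in the R+12 window nearest the target day. When that sample exists, neither document lets a value from another visit override it.

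**The concern.** The protocol treats a first post-treatment value at or above LLOQ as a signal that needs a second sample. Note 3 treats it as the event. The SAP gives no reason for the difference and does not say that it departs from the protocol. Because it keeps confirmation for on-treatment failure, the omission looks like an oversight specific to relapse.

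Two planned outputs could then disagree about the same person: the relapse count and the SVR12 result. Program validation would not catch this, because it checks the code against the SAP, and a single-value rule would pass. SAP Version 2.0 intends the report to contribute to a joint manuscript, so the relapse count may be read away from the individual listings that would explain it.

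**Working it through.** The plan states no figure for this point, so there is none to reproduce. The check applies the rules, as written, to the possible result sequences.

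**Inputs**
- Relapse rule: SAP 4.4.2, Note 3.
- Confirmation requirement: Protocol 6.2.4 and 7.3.
- SVR12 rule: Protocol 9.2.1.1 and SAP 4.3.1, Note 1.
- Visit windows (SAP 2.6): R+4 is R+23 to R+35, R+12 is R+79 to R+98, R+24 is R+161 or later.
- Turnaround: routine results within 2–3 weeks of specimen receipt (Protocol 6.3.8); repeat sample within a further 2 weeks (Protocol 6.2.4).
- Participants: 7 in total (SAP 2.1). The split by arm is not given.

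**Step 1. Apply the rules.** Every participant here is below LLOQ at the last result before end of treatment and attends all three post-treatment visits. A minus is below LLOQ and a plus is at or above LLOQ; brackets give the repeat sample.

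| Sequence | R+4 | R+12 | R+24 | Relapse, SAP Note 3 | Relapse, if confirmation is required | SVR12 |
|---|---|---|---|---|---|---|
| A | + (repeat −) | − | − | yes | no | responder |
| B | − | − | + (repeat −) | yes | no | responder |
| C | − | − | + (repeat +) | yes | yes | responder |
| D | − | + (repeat −) | − | yes | no | failure |

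A and B carry both labels only because Note 3 omits confirmation. C carries both under either rule. D shows what a confirmed-only rule does at R+12: an SVR12 failure that is not a relapse.

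**Step 2. Enumerate.** Each visit can be −, + with repeat −, or + with repeat +. With R+12 below LLOQ, R+4 and R+24 give 3 × 3 = 9 sequences. Removing the one with no positive value leaves 9 − 1 = 8 that meet Note 3 and are also SVR12 responders. Three of the 8 contain no confirmed value, and requiring confirmation removes the relapse label from all three. The other 5 contain a confirmed value and keep both labels: 2 are confirmed at R+24 only, and 3 have a confirmed value at R+4. These are logical possibilities, not probabilities.

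**Step 3. Check the timing of the repeat** (shipping time ignored).
- First sample at R+4, day 4 × 7 = 28: result by 28 + 21 = day 49, repeat by 49 + 14 = day 63. This is before the R+12 window opens on day 79.
- First sample at R+12, day 12 × 7 = 84: result by 84 + 21 = day 105, repeat by 105 + 14 = day 119. The window closes on day 98, so the repeat can fall outside it. A repeat inside the window would still be further from day 84 than the first sample, so the first sample decides SVR12, as in D.

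**Step 4. Size.** If no other participant relapses, one participant with sequence A moves 4.4.2(d) from 0 to 1 among the 7. The SVR12 numerator is the same under either relapse rule, so the 90% Wilson and 95% Clopper-Pearson intervals are also the same.

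**The case against.** The strongest reply is that the two documents describe the same pattern. Protocol 6.2.4 defines the evidence of relapse by two results and then imposes a sampling duty; Note 3 restates the two results. This is right as far as it goes: the gap is a requirement that was not carried over, and the two definitions do not compete. But Protocol 7.3 says the second measurement is there to confirm relapse, and a count that ignores it does not follow the protocol.

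A second reply is that SVR4 and SVR12 also rest on single samples, so Note 3 at least matches them, and a confirmed-only rule creates the opposite mismatch in sequence D. That stands, and the fix has to say how D is reported.

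A reader might infer that missing confirmation is the only source of double labels, and that adding it would make the relapse and SVR12 results agree. Sequence C shows otherwise. For a confirmed late relapse both labels are correct, because they describe different time points.

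Finally, the stakes are low. Item (d) is a count with no percentage or interval. Relapse is not among the outcome measures in Protocol 9.2. The final report is descriptive and consists mainly of listings, and 4.4.2(a) lists every HCV RNA result by participant. All of this stands and sets the severity.

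**Conclusion.** The point holds as a minor one. Note 3 can count a transient, unconfirmed value as a relapse in a participant who is an SVR12 responder. The effect is one added relapse for each such participant, for example 0 to 1 among 7. This assumes that the rule is programmed as written and that such a value occurs; the documents give no rate for it.

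Three stronger readings are not supported:
- A reader might infer a large shift in relapse proportions by arm. The documents give no split of the 7 participants, item (d) plans no percentage, and the planned 20 per arm no longer applies.
- A reader might infer that the primary result is affected. The SVR12 rule and its intervals do not use the relapse variable.
- A reader might infer that the count also needs correcting for reinfection, since a genotype sample is taken at failure. The plan sets no such step for relapse on study. All participants enter with genotype 1, so a change of genotype could not reveal reinfection with the same genotype. A separate reinfection row is optional and is not part of this point.

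**What to change.** In SAP 4.4.2, Note 3, define relapse as HCV RNA below LLOQ at the last result before end of treatment, followed after treatment by a value at or above LLOQ that is confirmed on a second sample as in Protocol 6.2.4. Add three reporting rules:

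- Flag separately, outside the count in (d), any post-treatment value at or above LLOQ that has no confirmatory sample or has a repeat below LLOQ. If that value is the R+12 sample, the participant remains an SVR12 failure, with the reason given under 4.3.1(c).
- Report a confirmed relapse after an R+12 value below LLOQ as relapse after SVR12.
- Footnote any participant with a confirmed value at R+4 and an R+12 value below LLOQ, since both labels would still apply.

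Leave the SVR12 definition unchanged. The cost is one amended sentence, these short rules, and an update to the relapse program and its validation. The confirmatory samples are already required by the protocol.
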